9.4 Reporting Procedure for Serious Adverse Event

Serious adverse events that occur beginning with the signing of the informed consent form, or within 30 days of the individual undergoing prostate biopsy must be reported to the University Hospitals Principal Investigator.

10. RECORDS/DATA TO BE KEPT

10.1 Regulatory Considerations

The study will be conducted in compliance with ICH guidelines and with all applicable federal (including 21 CFR parts 56 & 50), state or local laws.

10.2 Written Informed consent

Provision of written informed consent will be obtained prior to any study-related procedures. The Principal Investigator will ensure that the subject is given full and adequate oral and written information about the nature, purpose, possible risks and benefits of the study as well as the subject's financial responsibility. Subjects will also be notified that they are free to discontinue from the study at any time. The subject will be given the opportunity to ask questions and allowed time to consider the information provided.

The consent will take place at the clinical practices of the listed co-investigators in a private location. The patients will be evaluated a second time for MR safety prior entering the magnet prior to each MRI examination.

The original, signed written Informed Consent Form will be kept with the Research Chart in conformance with the institution's standard operating procedures. A copy of the signed written Informed Consent Form will be given to the subject.

10.3 Subject Data Protection

In accordance with the Health Information Portability and Accountability Act (HIPAA), a subject must sign an authorization to release medical information to the sponsor and/or allow the sponsor, a regulatory authority, or Institutional Review Board access to subject's medical information that includes all hospital records relevant to the study, including subjects' medical history.

10.4 Accessing Electronic Medical Records for University Hospitals Health System

This study will access electronic medical records systems to obtain medical information for the subjects enrolled in this study. We seek a HIPAA waiver to identify eligible patients and check whether patients meet inclusion criteria before approaching them for the study (see Recruitment section 4.1).

In order to ensure patient safety, investigators and study personnel must have up-to-the minute health information for subjects enrolled to this study. Therefore, electronic medical records must be utilized to obtain medical information in a timely manner. The following electronic systems will be used: IDX program to access scheduling information; UH Physician Portal/EMR/AEMR to access lab results and physician notes; PCOSS LITE as necessary to locate archived medical records; COPATH to locate archived pathology records; PACS to access radiological imaging results; and MySecureCare (Sunrise Clinical Manager) to access some or all of the above information when this application is fully functional.

Access to these systems is required for the life of this research study. Information obtained from electronic systems will be copied into the research chart and/or printed (lab results, physician notes, etc.) and stored in the research chart. Research charts are kept secure and destroyed according to UH policy.

The PI, co-investigators, study coordinator, and/or data manager for this study via password-protected login will obtain study data. The coordinator will be assessing EMR to obtain spontaneous adverse events. All study personnel involved in this research will adhere to the UH policies regarding confidentiality and Protected Health Information.

Patient MRI images will be de-identified to protect personal information and will only referred to by a unique number identifier.

Research MRI and MRF images may be reconstructed or analyzed in either an online or offline manner. If images are reconstructed online, it is possible to share these images with referring physicians or radiologists using the PACS database. If requested and available online, these images may be shared via PACS. However, there may be no direct benefit of sharing these research images.

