Request for waiver of HIPAA authorization and waiver of consent: We are requesting a waiver of HIPAA authorization and waiver of consent for identifying and contacting patients in person and not a waiver of the consent for the research study as such. We intend to identify patients from physician portal, inpatient/outpatient MRI schedule and/or referred by treating physician for a clinically indicated breast MRI and contact them in person. There will be no improper use of or disclosure of PHI under this waiver. The investigator will take precautions to protect the subject's privacy and the confidentiality of the data pertaining to his/her participation in this research study. Only the research staff will access the PHI for above described purpose. The patient identifiers accessed under this waiver of HIPAA authorization will not be retained. The identifiers will be destroyed on the same day once the purpose of contacting the patients in person is complete. We assure that the PHI will not be reused or disclosed to (shared with) any other person or entity, except as required by law, for authorized oversight of the research study, or for other research for which the use or disclosure of the PHI would be permitted under the Privacy Rule. We are requesting a waiver of HIPAA authorization for contacting the patients in person and not a waiver of informed consent process for the study itself. For this purpose, the waiver of HIPAA authorization and waiver of consent is necessary for recruitment. We will not be able to meet our recruitment goals without this waiver.

Inclusion and exclusion criteria will be assessed for each potential study patient, and written informed consent will be obtained by qualified study personnel in a private setting at UHCMC.

We will also obtain contact information of the patients to schedule them for follow-up scans for assessing tumor response. We hope to get at least one-two eligible patients per week and recruit patients over the first eighteen months. Since the chemotherapy regime takes about 4-6 months to complete followed by surgery, we hope to get the complete information for the last patient recruited within 2 years of initiating the study

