4.4 Methods

4.4.1 Breast MRI:

This is a prospective, longitudinal study comprising of pre-treatment baseline scan, interim scan after one cycle of chemotherapy and end-of-chemootherapy scans. The research sequence being evaluated is 3D MR Fingerprinting sequence. This is a painless technique that takes about 6 minutes to perform and does not have any risks or discomfort other than those associated with regular breast MRI. 3D MR Fingerprinting technique is also a non-contrast technique and generates quantitative information about MR-visible tumors without having to administer contrast. Since we propose to add 3D MR Fingerprinting sequence to regular clinical MRI scans ordered as part of standard of care, this would only add approximately 20 minutes to overall scan time. For patients who undergo research only 3D MR Fingerprinting scans, the entire scan time would be approximately 30 minutes, less than the time taken for regular clinical MRIs. All patients would be screened for MR Safety and Eligibility to eliminate any risks of undergoing MRI. For patients getting contrast (Gadavist®) for research purposes, the eGFR would be checked from patient records and contrast would only be administered to patients who have a documented eGFR > 40 ml/min/1.73 m² within the previous 3months.

4.4.2 Study procedures:

Radiology study personnel will obtain consent in the Radiology department prior to performing 3D MR Fingerprinting scans. Consent to participate will be obtained prior to performing any research scans:

Visit 1: 3D MR Fingerprinting images will be added to the clinical MRI scan before start of chemotherapy or before surgery for the MammaPrint cohort. The additional research images will take less than 20 minutes to acquire.

Visit 2: Patients receiving chemotherapy will be scheduled for a research only non-contrast 3D MR Fingerprinting and anatomical MRI scans 7- 10 days after the first cycle of chemotherapy. Acquisition of images will take approximately 30 minutes.

Visit 3: For patients receiving chemotherapy, if the treating physician orders a clinical MRI scan within 1 month of end of chemotherapy treatment, we will add a 3D MR Fingerprinting sequence to the clinical scan. The additional research images will take less than 20 minutes to acquire.

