6. STATISTICAL CONSIDERATIONS

1. From the 3D MR Fingerprinting maps, T1 and T2 relaxation times will be obtained for tumor, and peritumoral and normal breast tissue at all three scans.
2. From routine MRI scans, the tumor size and tumor ADC will be obtained.
3. Changes in all quantitative measurements will be compared between responders and non-responders based on final surgical pathology and the predictive value of 3D MR Fingerprinting as compared to existing techniques would be assessed using appropriate t-tests and logistic regression analysis.

Sample Size Calculation: Based on our pilot data, we expect a 25% change in T1 and T2 relaxation times in responders and less than 7% change in non-responders with an effect size of 18% (0.18). At a significance level of 0.05 and power of 80%, the expected sample size is 62. Based on our pilot data, we also expect an attrition and drop-out rate of 50%, and thus total number of subjects recruited will be 124.

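### Section 10.4 lets treating physicians obtain research MRF images at any time, so the Visit 2 maps can reach the treating team months before the pathology they are meant to predict

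*Combined protocol and SAP*

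**What the plan says.** Section 10.4 deals with research MRI and MRF images, which may be reconstructed online or offline. For the online case it says: "If images are reconstructed online, it is possible to share these images with referring physicians or radiologists using the PACS database". It continues: "If requested and available online, these images may be shared via PACS. However, there may be no direct benefit of sharing these research images". It names no visit, no embargo date and no record of releases.

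The other relevant provisions are these:

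- **Timing of the early scan (Section 4.4.2).** At Visit 2, patients receiving chemotherapy have "research only non-contrast 3D MR Fingerprinting and anatomical MRI scans 7- 10 days after the first cycle of chemotherapy".
- **Length of treatment (Section 4.1).** "Since the chemotherapy regime takes about 4-6 months to complete followed by surgery".
- **Outcome (Section 4.4.2, response criteria).** Response is read from the final surgical pathology. Patients who do not reach surgery are classified by RECIST 1.1 instead.
- **Analysis (Section 6, item 3).** "Changes in all quantitative measurements will be compared between responders and non-responders based on final surgical pathology". The methods named are t-tests and logistic regression.
- **Treatment data (Section 5).** The chemotherapy schedule and regimen and the date of surgery are collected. Section 6 does not say how they will be used.

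**The concern.** A study of whether an early test predicts a later outcome needs the care between the two to be unaffected by the test. Here the referring physician may obtain the index-test images during that interval. If a map showing little early change leads to a different course of treatment, the pathology reflects the altered care, and the link between T1/T2 change and response is no longer the one the study set out to measure.

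This differs from masking the image readers to pathology. Masked readers would not help, because the route runs from the test to the treating team and then to the outcome.

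At stake is the central comparison in Section 6. Only patients whose images were requested and acted on would be affected, so the distortion would be selective. As written, the plan would leave no trace of who those patients were.

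**Working it through.** **1. Is the route open?** No figure in the plan belongs to this point, so the check is of the text.

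- Index images available: 7-10 days after cycle 1 (Section 4.4.2).
- Outcome available: after about 4-6 months of chemotherapy and then surgery (Section 4.1).
- Release rule: on request, if reconstructed online, with no time limit (Section 10.4).
- Content released: Section 1 describes the MRF output as quantitative T1 and T2 maps. A shared MRF image therefore carries the quantity under study, though not a report or a cut-off.
- Safeguards in the text reviewed: no embargo, no masking of the treating team, no release log, and no analysis in Section 6 that uses treatment changes.

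Most of the treatment lies ahead when the Visit 2 maps exist, and nothing in that text stops their release. The MammaPrint cohort has a single scan and no chemotherapy response to predict, so it is not affected.

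**2. Which way would the bias run?** The illustration below rests on assumptions. Section 6 gives mean changes of 25% and under 7% (taken here as 7%), alpha 0.05, power 80% and 62 evaluable patients. It gives no SD, test or group split. Assume a two-sided two-sample t-test with 31 per group. Then 80% power requires a standardised difference of 0.723, so SD = 18/0.723 = 24.9 points. This SD is solved back from the power statement and is not trial data.

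*Case A: treatment is changed and would-be non-responders become responders.* Let k patients with mean change 7 move into the responder group:

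- Responder mean = (31×25 + 7k)/(31 + k).
- Responder variance = 24.9² + [31k/(31 + k)²]×18².
- Power is recomputed with group sizes 31 + k and 31 − k.

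| k (assumed) | Responder mean | Difference from 7 | Power |
|---|---|---|---|
| 0 | 25.0 | 18.0 | 80% |
| 3 | 796/34 = 23.4 | 16.4 | about 71% |
| 6 | 817/37 = 22.1 | 15.1 | about 62% |
| 9 | 838/40 = 20.95 | 13.95 | about 52-53% |

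*Case B: chemotherapy is cut short and would-be responders with little early change are left with residual tumour.* Section 4.4.2 counts any residual tumour as non-response. Under the same normal model, responders whose change is below 7 have mean 25 − 24.9×φ(a)/Φ(a), with a = (7 − 25)/24.9 = −0.723, which is about −7.6. If k of them move to the non-responder group:

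- k = 2: responders (775 + 15.1)/29 = 27.2; non-responders (217 − 15.1)/33 = 6.1; difference 21.1.
- k = 4: responders (775 + 30.2)/27 = 29.8; non-responders (217 − 30.2)/35 = 5.3; difference 24.5.

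Case A shrinks the difference and Case B enlarges it. The documents give no basis for choosing between them or for any value of k.

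**The case against.** The strongest case on the other side is that the route is narrow. Sharing needs online reconstruction, a request, a change in care and then a changed pathology result. No report, threshold or interpretation is provided for. Section 10.4 also says that MRI images are de-identified and referred to only by a number, so patient-level sharing would need the images to be linked back. All of this bears on how often the route would be used. It does not close it, because the same section expressly permits the sharing.

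Four stronger readings are tempting, and the documents do not support them:

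- **That the bias must make MRF look worse.** Case B shows that the opposite is equally possible.
- **That no analysis could deal with it.** The regimen and surgery date are collected, and the protocol is silent on logging requests rather than ruling it out. What stands is narrower: regimen data alone cannot show which changes followed sight of an MRF image.
- **That the protocol encourages treatment changes based on MRF.** The remark in Section 1 about ineffective cycles is background on the limits of size criteria. No text reviewed says that MRF will guide care.
- **That power will fall to some stated level.** The converted counts, the even split and the SD are all assumed.

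The text between the Table 1 caption in Section 2 and Section 4.1, and the consent pages, were not available for this review. A statement there on use of results cannot be excluded. If it exists, it would have to be reconciled with Section 10.4.

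**Conclusion.** The point holds as a design weakness that is cheap to remove. The plan does more than omit a detail: it gives a permission without a time limit, and for the chemotherapy cohort this covers the months between the early index scan and the outcome. If released images alter care, the outcome is no longer independent of the test. The direction of the bias is unknown and its size cannot be estimated from the documents; the figures above show only that a few affected patients in a sample of 62 could move the result either way. The conclusion assumes that some images would be requested and acted on, which the protocol neither states nor prevents. Label: cheap improvement, moderate confidence.

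**What to change.** Amend the sharing paragraph of Section 10.4 along these lines:

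> For the chemotherapy cohort, research MRF maps and T1/T2 values from Visits 1 and 2 are not released to the treating team or to clinical PACS until final surgical pathology is recorded or, where there is no surgery, the end-of-treatment response assessment. Standard-of-care clinical MRI images and reports are unaffected. Research anatomical images may still be reviewed, and unexpected safety findings communicated. Any earlier release of MRF maps or values is logged with its date, visit and recipient role.

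The explicit exemption for clinical images matters because at Visit 1 the MRF sequence is added to the clinical scan.

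Add to Section 6 a sensitivity analysis that repeats the main comparison without patients whose maps or values were released early. Use the regimen and surgery-date data already collected to identify treatment changes after release. Requests are unlikely to be random, so this analysis is a check and does not replace the hold.

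The cost is one paragraph, a PACS routing setting and a short log. The downside is that physicians cannot see on-treatment MRF maps on request. The protocol's own view of that benefit is: "However, there may be no direct benefit of sharing these research images".

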10.5 Retention of records

The Principal Investigator of The Case Comprehensive Cancer Center supervises the retention of all documentation of adverse events, case report forms, source documents, records of study drug receipt and dispensation, and all IRB correspondence for as long as needed to comply with national and international regulations and the institution in which the study will be conducted, or for the period specified by the sponsor, whichever is longer. No records will be destroyed until the Principal Investigator confirms destruction is permitted.

10.6 Audits and inspections

Authorized representatives of the sponsor, a regulatory authority, an Independent Ethics Committee (IEC) or an Institutional Review Board (IRB) may visit the Center to perform audits or inspections, including source data verification. The purpose of an audit or inspection is to systematically and independently examine all study-related activities and documents to determine whether these activities were conducted, and data were recorded, analyzed, and accurately reported according to the protocol, Good Clinical Practice (GCP), guidelines of the International Conference on Harmonization (ICH), and any applicable regulatory requirements.

10.7 Data Safety and Monitoring Plan

This protocol will adhere to the policies of the Case Comprehensive Cancer Center Data and Safety Monitoring Plan in accordance with NCI regulations.

The group of investigators, including the principal investigator, and the research support staff will carry out the Data and Safety Monitoring Plan. Adverse events will not be submitted to an external Data and Safety Monitoring Board or Committee for assessment; instead, there will be an ongoing review of the aggregate data each month to ensure that the study can continue without undue risk to participants. Data will be reviewed to ensure that they are accurate, complete, and that data collection is in compliance with the protocol.

There will also be a continual assessment of the risks and benefits through the review of individual adverse events and other safety parameters as they occur throughout the study to determine whether individual participants can safely continue to participate. Serious adverse events, should any occur, will be reviewed within 48 hours of occurrence with a determination made for medically appropriate follow-up for the subject involved. Adverse event reporting will be strictly performed in compliance with IRB rules for reporting.

References

3. Virostko J, Hainline A, Kang H, et al. Dynamic contrast-enhanced magnetic resonance imaging and diffusion-weighted magnetic resonance imaging for predicting the response of

locally advanced breast cancer to neoadjuvant therapy: a meta-analysis. *J Med Imaging* (Bellingham). 2018 Jan;5(1):011011

